Lymphomagenesis is known to be a result of aberrant signaling through the B-cell receptor (BCR). Several models have highlighted specific checkpoints that appear to be regulators of downstream signal propagation leading to abnormal nuclear transcription within the lymphocyte leading to either anti-apoptosis or a proliferative advantage. A better understanding of the BCR signaling pathway in malignant lymphocytes has led to several small molecule inhibitors entering clinical practice as single agents for the treatment of non-Hodgkin lymphoma (NHL). Two classes of BCR antagonists have shown strong activity in (NHL): Bruton's Tyrosine Kinase (BTK) and phosphoinositide-3kinase (PI3-K) delta inhibitors. Ibrutinib is a first generation selective and irreversible inhibitor of BTK. umbralisib (formerly known as TGR-1202) is a PI3-K delta inhibitor with a novel structure unlike other PI3K inhibitors affording once daily dosing and to date a unique toxicity profile. Attacking the aberrant BCR signaling pathway at separate nodes may be an important mechanism to overcome chemorefractory NHL. This is a single-center Phase IIa study evaluating the safety and tolerability of umbralisib and Ibrutinib in patients with relapsed or refractory diffuse large Bcell lymphoma (DLBCL). We plan to accrue 24 patients. The primary endpoint in this phase IIa study is to consecutively monitor the safety and tolerability of the oral doublet and allow a preliminary assessment of the efficacy of this novel combination to provide background for an appropriately powered phase II or phase III study. There will be 3 treatment groups given one year (12 months) of therapy. Group A (consented to optional biopsies; 6 patients): umbralisib800 mg PO daily on Days 1-8; then umbralisib 800 mg oral daily and Ibrutinib 560 mg oral daily; Group B (consented to optional biopsies; 6 patients): Ibrutinib 560 mg PO daily Days 1-8; then umbralisib 800 mg PO daily and Ibrutinib 560 mg PO daily; and Group C (deferred consent to optional biopsies or consented to optional biopsies; 12 patients): umbralisib 800 mg PO daily and Ibrutinib 560 mg PO daily. Secondary endpoints of the trial will be assessment of the overall response rate (ORR) defined as the sum of complete responses (CR) and partial responses (PR) and to determine the progression-free survival (PFS), time to response (TTR), and duration of response (DOR) in patients with relapsed or refractory DLBCL.

Page 4 of 65

Schema:

Title: A Single-center Phase IIa Study Evaluating the Safety and Tolerability of Umbralisiband Ibrutinib in Patients with Relapsed or Refractory Diffuse Large B-cell Lymphoma

Group A (consented to optional biopsies; 6 patients): umbralisib 800 mg PO daily on Days 1-8; then umbralisib 800 mg oral daily and Ibrutinib 560 mg oral daily

Group B (consented to optional biopsies; 6 patients): Ibrutinib 560 mg PO daily Days 1-8; then umbralisib 800 mg PO daily and Ibrutinib 560 mg PO daily

Group C (deferred consent to optional biopsies or consented to optional biopsies; 12 patients): umbralisib 800 mg PO daily and Ibrutinib 560 mg PO daily

Duration of therapy

In the absence of treatment delays due to adverse event(s), treatment should continue unless one of the following criteria applies:

- Disease progression or inter-current illness that prevents further treatment.
- Patient decides to withdraw from the study, or changes in the patient's condition render the patient unacceptable for further treatment in the judgment of the investigator.
- One year of therapy

A cycle is 28 days of treatment with any oral agent regardless of group assignment. The first efficacy assessment should be approximately 8 weeks after Cycle 1/Day 1 (+/- 7 days). Thereafter efficacy assessment will occur approximately every two months until 6 months then every 3 months until completion of 12 months of treatment (+/- 7 days). After Month 12, efficacy assessments should occur at the investigators discretion.

Section 1.0 Objectives:

Primary objective:

- 1. To determine the safety and tolerability of umbralisib and ibrutinib in relapsed and refractory (rel/ref) DLBCL Secondary objectives:
 - 1. To determine the overall response rate (ORR) defined as the sum of complete responses (CR) and partial responses (PR).
 - 2. To determine the event-free survival (EFS), time to response (TTR), and duration of response (DOR) in patients with rel/ref DLBCL.

Exploratory objectives:

- 1. To evaluate molecular profiling of patient samples (optional lymph node biopsies) obtained at days 0 (pretreatment; core biopsy), day 8 (fine needle aspiration) and end of treatment (progressive disease or end of study treatment—1 year; core biopsy) to evaluate the baseline characteristics and dynamic shifts in mutational landscape, transcriptional signatures and intracellular signaling cascades in primary tumor cells.
 - (i) Next generation sequencing to define the mutational status of 384 genes that mutated in DLBCL, including CD79B, CARD11, and MYD88;
 - (ii) Transcriptional profiling to evaluate signatures of B-cell receptor signaling and the back-up pathway of oxidative phosphorylation.
 - (iii) Phospho-specific flow cytometry to measure the basal and induced level of activation of components within parallel signaling pathways downstream of the B-cell receptor.
 - (iiii) Monitor changes in T- cell characteristics in response to exposure to umbralisib and ibrutinib
- 2. To perform quantitative response evaluation by peripheral blood cell-free DNA sequencing at enrollment, day 8, 1 month, at every response assessment time point compared to standard radiographic response evaluation by PET/CT or CT and end of treatment (progressive disease or end of study treatment—1 year). After month 12, efficacy assessments should occur at the investigators discretion with collection of a research blood sample only if feasible.
- 3. To evaluate the genetic profiling for drug resistance mutations
- 4. To evaluate DLBCL subtype analysis by immunohistochemistry compared to Nanostring assessment

Section 2.0 Introduction:

2.1 Diffuse Large B-cell Lymphoma

Diffuse large B-cell lymphoma (DLCBL) remains the most common non-Hodgkin lymphoma (NHL) diagnosed per annum with an increasing prevalence, now noted to be approximately 500,000 individuals (http://seer.cancer.gov/stat/facts/html/leuks.html). Nearly 40% of those individuals are older than 70 years of age. Patients with DLBCL presents most commonly with advanced stage disease and without treatment are nearly uniformly lethal. However current multiagent immunochemotherapy regimens do provide a curative option for those able to receive treatment. The most common combination chemo-immunotherapy is R-CHOP (rituximab, cyclophosphamide, doxorubicin, vincristine, prednisone), which now cures nearly two-thirds of patients.(1) The prognosis is dependent on many patient specific factors most accurately defined by the International Prognostic Index (IPI) and by recent disease specific characteristics defined as molecular subtyping into either Germinal Center B-cells (GCB) or Activated B-cell like (ABC).(2, 3) In the current treatment era the overwhelming majority of patients will be exposed to a rituximab containing induction regimen. Despite aggressive up front treatment nearly one-third of patients with DLBCL will have refractory disease or experience a relapse of DLBCL. A second chance at cure is maintained with second line therapy in addition to high dose therapy and autologous stem cell rescue (HDT-ASCR) in those who are transplant eligible. However, only 1 in 4 patients who undergo transplant will achieve long-term disease control and subsequent chemotherapy regimens yield diminishing returns and often serve as a bridge towards allogeneic transplantation if eligible and/or available.(4) Patients who are not considered transplant eligible suffer a dismal prognosis with no

standard of care to help guide treatment choices. Therefore, a substantial number of highly chemotherapy refractory patients remain in search of further therapy that can preserve the balance of quality and quantity of life.

[figure not shown]
2.2 B-cell receptor Pathway

The B-cell receptor pathway is a complex network of enzymatic checks and balances that regulate B-cell maturation and subsequent migration.(5) Many points of divergence exist within the network creating parallel streams of potential reflexive regulation. Tonic stimulation of an enzymatic node by mutations within the protein can be a lymphoma generating event. This has been further expounded by the molecular profiling of DLBCL. The results have led to the defining of 3 different molecular subtypes of DLBCL in which the BCR pathway plays a significant role: 1) Germinal Center B-cell (GCB), 2) Activated B-cell like (ABC), and 3) Unclassifiable.(3) The GCB subtype is felt to be more attracted to the phosphoinositol-3 kinase pathway.(6) The ABC subtype of DLBCL appears to be addicted towards the downstream pathway leading towards the Nfk-B stimulation and subsequent nuclear transcription.(7) The GCB subtype of DLBCL represents nearly two-thirds of all DLBCL cases and has a more favorable prognosis than ABC DLBCL. These downstream pathways have become clinically relevant targets with several drugs attempting to inhibit these processes.

2.3 Targeting the B-cell receptor pathway

Success with small molecule inhibitors that abrogate the abnormal signaling through the BCR pathway has brought upon an exciting paradigm shift in the management of B-cell NHL. Several novel non-chemotherapeutic drugs now attack the malignant lymphocytes via mechanisms unperturbed or selected for by prior non-selective chemotherapy or exposure to CD20 directed monoclonal antibodies (Figure 1). Currently these drugs are in the clinic as single agents

or combined with a CD20 monoclonal antibodies (Figure or combined with a CD20 monoclonal antibody. This includes but not limited to the Bruton's tyrosine kinase (BTK) inhibitor ibrutinib and the PI3-K inhibitor, Idelalisib. Both BTK and PI3-K have several next generation antagonists in clinical development. Umbralisib_is a next generation PI3-K delta inhibitor with a novel structure different than other PI3-K inhibitors in development. This structure may lead to differential activity and toxicity profile than previously seen in other PI3-K inhibitors. Current data supports that BTK inhibitors may provide selective activity towards the ABC subtype of DLBCL whereas PI3-K inhibitors may provide selective activity to the GCB subtype of DLBCL.(8)

(PI3K6) are shown. It can also be seen that signaling into the PI3K pathway can occur

upstream of the ibrutinib target, BTK, allowing activation of this important survival pathway in the presence of BTK inhibition (green arrows). This provides a rationale for dual

inhibition of these parallel pathways.

TGR-1202

Currently targeted agents against the BCR have been primarily explored as single agents or in combination with a CD20 monoclonal antibody. Results have shown that as

a single agent each may be potent enough to achieve disease control in indolent NHL, like follicular lymphoma (FL) and chronic lymphocytic leukemia/small lymphocytic lymphoma (CLL/SLL).(9) However, treatment of relapsed/refractory (rel/ref) DLBCL especially after HDT-ASCR or in transplant ineligible patients remains a difficult situation with a poor overall prognosis. Combinations of novel agents that do not have cumulative toxicities are likely needed to overcome the clonal complexity and aggressive biology that prevents durability in the rel/ref DLBCL. The novel chemo-free oral combination of umbralisib and Ibrutinib may be an attractive combination for the treatment of this difficult to treat population.

[figure not shown]
2.4 Rationale for a phase IIa design

[figure not shown]
Both BTK and PI3-K inhibitors that are in current practice have been developed under a continuous dosing scheme in an attempt to chronically antagonize the BCR pathway. As drugs progress through phases of clinical trials it is well established dogma that a maximum tolerated dose (MTD) is the objective in phase I studies. However, this only reports

dose limiting toxicities (DLT) during the initial cycle of therapy when further cumulative toxicities may be seen in subsequent cycles that limits the utility of a regimen. Therefore, in paradigms were long-term safety and tolerability is paramount and needed to balance with objective responses phase IIa studies can be employed to not only provide this tolerability signal but inform future studies that lead to appropriately powered and better informed phase II or phase III studies. Therefore, we must balance efficacy while limiting cumulative toxicities events (CTE).

2.1 Umbralisib

Umbralisib (formerly known as TGR-1202) is a highly specific and orally available PI3K delta inhibitor with high selectivity over the alpha, beta, and gamma isoforms of PI3K. The delta isoform of PI3K is highly expressed in cells of hematopoietic origin, and strongly upregulated, and often mutated in NHL. Umbralisib has demonstrated safety in an ongoing Phase I clinical trial in patients with NHL and chronic lymphocytic leukemia (CLL).(10) umbralisib is manufactured by Alembic Pharmaceuticals and is being supplied by TG Therapeutics, Inc.

2.1.4 Clinical development of TGR 1202 in hematologic malignancies

2.1.4.1 Umbralisib monotherapy

Umbralisib is being evaluated in multiple studies. The first in human phase I dose-escalation study with expansion cohorts in rel/ref hematologic malignancies patients has accrued approximately 55 patients. Umbralisib at doses ranging from 50 mg to the micronized 1800 mg QD dose has been tested. umbralisib is available as 200 mg tablets, as this study progressed to higher dose levels this resulted in an unfavorable number of tablets for daily administration. In an effort to improve the oral bioavailability of umbralisib and pill count, the particle size of the drug product was reduced through a micronization process. The micronization process resulted in greater absorption (approximately 3 fold in a 24 patient healthy volunteer bioequivalence study).

In this study adverse events (AEs) have been manageable, with Grade 3/4 AEs occurring in >10% of patients consisting of the following (March 2015) regardless of attribution to umbralisib: neutropenia, rash, dyspnea, thrombocytopenia, and diarrhea. Of note, a Grade 3 AE of rash was reported in a patient in the non-micronized 800 mg dose cohort who was on concomitant antibiotics. This patient had a history of antibiotic related rash. All medications were held until the rash resolved and they were re-challenged at the 800 mg dose of umbralisib with no recurrence of rash. However, this event met the criteria for a DLT as stated in the protocol and subsequently 3 additional patients were treated at the 800 mg dose, with no additional DLT's reported.

Page 9 of 65

On this study the safety data has now been obtained on patients dosed with umbralisib daily for over a year with no safety concerns recognized or reported as documented by the Study Chair and Medical Monitor for the trial up through the micronized 1200 mg QD dose. Dosing continues in this study using the micronized formulation of umbralisib.

2.1.4.2 Umbralisib + anti-CD20 monoclonal antibody, ublituximab

Umbralisib continues to be evaluated in the phase 1/1b dose escalation study with the glycoengineered anti-CD20 monoclonal antibody ublituximab (UTX).(10) Fifty-seven patients have been enrolled and are evaluable for safety. AEs (AE; all causality) include: Day 1 infusion related reactions, neutropenia, diarrhea, nausea. To date, umbralisib related hepatotoxicity has not been reported in this study. No DLTs have occurred in the NHL cohort. A possible doseresponse relationship has been observed between "lower" and "higher" umbralisib doses. A higher dose was defined as greater than 800 mg of the non-micronized umbralisib. To date, 89% of pts (16/18) in the "high" dose cohorts remain on study progression free compared to 57% (8/14) in the "low" dose cohorts. This study continues to enroll in expansion cohorts in NHL subtypes with umbralisib at a micronized dose of 800 and 1200 mg plus UTX.

2.2 Ibrutinib

Ibrutinib is indicated for the treatment of: 1) patients with chronic lymphocytic leukemia (CLL) 2) patients with chronic lymphocytic leukemia (CLL) with 17p deletion; 3) patients with mantle cell lymphoma (MCL) who have received at least one prior therapy (accelerated approval was granted for this indication based on overall response rate, continued approval for this indication may be contingent upon verification of clinical benefit in confirmatory trials; 4) patients with Waldenström's macroglobulinemia (WM). 5) Chronic graft versus host disease (cGVHD) after failure of one or more lines of systemic therapy. Ibrutinib is not approved in the disease state being studied here.

2.2.1 Chemical structure and description of Ibrutinib

Ibrutinib is 1-[(3R)-3-[4-amino-3-(4-phenoxyphenyl)-1H-pyrazolo[3,4-d] pyrimidin-1-yl]-1-piperidinyl]-2-propen-1-one and has a molecular weight of 440.50 g/mole (anhydrous basis). Ibrutinib is a white to off-white crystalline solid. It has a single chiral center and is the R-enantiomer. The investigational drug product, ibrutinib, is an oral formulation containing micronized ibrutinib. Ibrutinib is manufactured by Pharmacyclics, Inc. and is being supplied by Janssen Scientific Affairs, LLC.

2.2.2 In vitro data of ibrutinib

In vitro studies have shown that ibrutinib binds covalently to a cysteine residue (Cys-481) in the BTK active site, leading to potent and irreversible inhibition of BTK enzymatic activity.(12) In cellular signal transduction assays with a B-cell lymphoma cell line, ibrutinib inhibited autophosphorylation of both BTK and phosphorylation of BTK's physiological substrate, phospholipase-C gamma (PLCγ).22 In DLBCL cell lines ibrutinib inhibited the proliferation at a median effective concentration of 1 to 2 nM.(13)

2.2.3 Pharmacology/Toxicology

Ibrutinib's bioavailability is relatively low and quite variable. A mass-balance study (PCI-32765CLL1004) demonstrated that ibrutinib 140 mg (admixed with 14C-ibrutinib) showed approximately 90% of radioactive ibrutinib was excreted within 168 hours after administration, with less than 10% accounted for in urine and the remainder in feces. A negligible fraction was excreted as unchanged drug.

Ibrutinib is metabolized in the liver. In a hepatic impairment study, data showed an increase in ibrutinib exposure. Following single dose administration, the AUC of ibrutinib increased 2.7-, 8.2- and 9.8-fold in subjects with mild (Child

-Pugh class A), moderate (Child-Pugh class B), and severe (Child-Pugh class C) hepatic impairment compared to subjects with normal liver function. The safety of ibrutinib has not been evaluated in patients with hepatic impairment. Monitor patients for signs of ibrutinib toxicity and follow dose modification guidance as needed. It is not recommended to administer ibrutinib to patients with moderate or severe hepatic impairment (Child-Pugh classes B and C).

Ibrutinib is metabolized primarily by CYP3A. Drug-drug interaction study has demonstrated that when ibrutinib was administered at a 120 mg dose in combination with 40 mg of ketoconazole, a strong CYP3A inhibitor, the last concentration quantifiable (AUCO-last) was extended up to 29 times longer than without ketoconazole exposure. Terminal half-life was not increased. Therefore, use of strong CYP3A inhibitors is not allowed and guidance on concomitant use of ibrutinib with other CYP3A inhibitors or inducers is provided in the Appendix A.

Absorption

lbrutinib is absorbed after oral administration with a median Tmax of 1 to 2 hours. Ibrutinib exposure increases with doses up to 840 mg. The steady-state AUC (mean \pm standard deviation) observed in patients at 560 mg is 953 \pm 705 ng·h/mL and in patients at 420 mg is 680 \pm 517 ng·h/mL. Administration with food increased ibrutinib Cmax and AUC by approximately 2 to 4- and 2-fold, respectively, compared with administration of ibrutinib after overnight fasting.

Distribution

Reversible binding of ibrutinib to human plasma protein in vitro was 97.3% with no concentration dependence in the range of 50 to 1000 ng/mL. The volume of distribution at steady state (Vd,ss) was 683 L, and the apparent volume of distribution at steady state (Vd,ss/F) was approximately 10000 L.

Metabolism

Metabolism is the main route of elimination for ibrutinib. It is metabolized to several metabolites primarily by cytochrome P450, CYP3A, and to a minoextent by CYP2D6. The active metabolite, PCI-45227, is a dihydrodiol metabolite with inhibitory activity towards BTK approximately 15 times lower than that of ibrutinib. The range of the mean metabolite to parent ratio for PCI-45227 at steady-state is 1 to 2.8

Ibrutinib binds covalently and irreversibly to Cys-481 near the BTK active site and inhibits the enzymatic activity with a half maximal inhibitory concentration (IC50) of 0.5 nM. The binding site of Bruton's tyrosine kinase remained fully occupied by ibrutinib (\geq 90% occupancy) for at least 24 hours in subjects treated with ibrutinib doses of \geq 2.5mg/kg/day (\geq 175mg/day for average weight of 70kg. Although ibrutinib is rapidly eliminated from the plasma after oral administration, once daily dosing with ibrutinib is adequate to sustain maximal pharmacodynamic activity for 24 hours post-dosing. Therefore, 560 mg/day is adequate to achieve exposures yielding full BTK active-site occupancy in most patients.

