5.2.2 Guidelines for Administration of Ibrutinib

- Method of Administration: Ibrutinib 4 capsules each 140mg = 560mg will be administered orally once daily.
 Ibrutinib should be taken in the evening. (NOTE: After cycle 2 if no CTE have been seen then the patient can have the option to take umbralisib and Ibrutinib dosing together at the same time of day).
- Ibrutinib capsules should be swallowed whole with a full glass (approximately 8 ounces) of water. Ibrutinib capsules should not be opened, chewed or dissolved.
- Potential Drug Interactions: Avoid co-administration with strong or moderate CYP3A inhibitors and consider
 alternative agents with less CYP3A inhibition. Concomitant use of strong CYP3A inhibitors which would be
 taken chronically (e.g., ritonavir, indinavir, nelfinavir, saquinavir, boceprevir, telaprevir, nefazodone) is not
 recommended. For short-term use (treatment for 7 days or less) of strong CYP3A inhibitors (e.g., antifungals

and antibiotics) consider interrupting ibrutinib therapy until the CYP3A inhibitor is no longer needed [see Drug Interactions (7.1)]. Reduce ibrutinib dose to 140 mg if a moderate CYP3A inhibitor must be used (e.g., fluconazole, darunavir, erythromycin, diltiazem, atazanavir, aprepitant, amprenavir, fosamprevir, crizotinib, imatinib, verapamil, and ciprofloxacin) [see Drug Interactions (7.1)]. Patients taking concomitant strong or moderate CYP3A inhibitors should be monitored more closely for signs of ibrutinib toxicity.

- Also avoid grapefruit and Seville oranges during treatment, as these contain moderate inhibitors of CYP3A and can alter ibrutinib pharmacokinetics.
- For patients with mild liver impairment (Child-Pugh class A), the recommended dose is 140 mg daily (one capsule). Avoid the use of ibrutinib in patients with moderate or severe hepatic impairment (Child-Pugh classes B and C) [see Use in Specific Populations (8.7) and Clinical Pharmacology (12.3)]
- Pre-medications: None

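### Section 2.2.3 bars strong CYP3A inhibitors, but Section 5.2.2 and Appendix A, after advising avoidance, leave the ibrutinib hold optional for courses of up to 7 days

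*Combined protocol and SAP*

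**What the plan says.** Section 2.2.3 (Pharmacology/Toxicology) reports the ketoconazole interaction and concludes: "Therefore, use of strong CYP3A inhibitors is not allowed". It refers the reader to Appendix A only for other CYP3A inhibitors and for inducers.

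Section 5.2.2, which the treating physician uses for dosing, nevertheless covers strong inhibitors:

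- General advice: "Avoid co-administration with strong or moderate CYP3A inhibitors", with a prompt to look for less inhibiting alternatives.
- Chronic strong inhibitors: not recommended.
- Short courses: "For short-term use (treatment for 7 days or less) of strong CYP3A inhibitors" lead to the instruction to "consider interrupting ibrutinib therapy until the CYP3A inhibitor is no longer needed". No reduced dose is given.
- Moderate inhibitors: "Reduce ibrutinib dose to 140 mg if a moderate CYP3A inhibitor must be used".
- Patients on either class are to be watched more closely for ibrutinib toxicity.

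Appendix A, headed as following the ibrutinib US label, gives the same instructions and adds that strong inhibitors needed chronically should be avoided. Exclusion criterion 12 in Section 3.2 excludes patients who require a strong inhibitor, but it applies at entry.

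**The concern.** The background section bars the combination. The dosing section discourages it, then leaves the decision to hold ibrutinib to the physician if a short course is given anyway. Both cannot be the rule, and the protocol does not say which governs.

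The strength of the instructions is also out of order. An unavoidable moderate inhibitor triggers a directive, while a short course of a strong inhibitor triggers only a suggestion.

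Patient safety is at stake, in a foreseeable situation. Section 5.3 calls for full supportive care including antibiotics, and the short-term strong inhibitors named in Appendix A are antifungals and antibiotics such as voriconazole, posaconazole and clarithromycin. A physician treating an infection would find a ban in one place and an optional hold in another.

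**Working it through.** **Step 1: the texts side by side.** The protocol states no figure for this rule that could be reproduced, so the first check is textual.

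| Situation on study | Section 2.2.3 | Section 5.2.2 and Appendix A |
|---|---|---|
| Strong inhibitor, 7 days or less | Not allowed | Avoid; if used, consider a hold |
| Strong inhibitor, chronic | Not allowed | Not recommended; Appendix A adds avoid |
| Strong inhibitor, longer than 7 days but not chronic | Not allowed | Avoid; no dosing instruction for ibrutinib |
| Moderate inhibitor, unavoidable | Referred to Appendix A | Cut to 140 mg |

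Continuing 560 mg through a 7-day strong-inhibitor course breaches Section 2.2.3 but not the fallback wording of Section 5.2.2. Exclusion 12 does not settle the matter because it acts at entry. The prohibited treatments in Section 5.3 do not include CYP3A inhibitors, so the ban is not restored there.

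**Step 2: scale from the protocol's own AUC ratios.** Inputs:

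- Strong inhibitor (ketoconazole, healthy volunteers): AUC 24-fold, Cmax 29-fold (Appendix A).
- Hepatic impairment, single dose: "the AUC of ibrutinib increased 2.7-, 8.2- and 9.8-fold in subjects with mild", moderate and severe impairment respectively (Section 2.2.3).
- Response to those hepatic ratios: "For patients with mild liver impairment (Child-Pugh class A), the recommended dose is 140 mg daily" for mild; avoid ibrutinib for moderate or severe (Section 5.2.2).

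Formula: ketoconazole AUC ratio divided by hepatic AUC ratio.

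- Against mild: 24 / 2.7 = 8.9
- Against moderate: 24 / 8.2 = 2.9
- Against severe: 24 / 9.8 = 2.4

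**Step 3: cost of a mandatory hold.** A 7-day course with once-daily ibrutinib misses up to 7 doses.

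- Share of one 28-day cycle: 7 / 28 = 25%
- Share of 12 cycles: 7 / (12 × 28) = 7 / 336 = 2.1%
- Share of 52 weeks: 7 / 364 = 1.9%

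**The case against.** The strongest reply is that the dosing text is not permissive. It first tells the physician to avoid strong inhibitors and seek alternatives; the hold is a fallback after that. A full interruption is also stricter than a dose cut, so the contrast with moderate inhibitors comes down to one word, consider. The same verb, avoid, is used for ibrutinib in moderate or severe hepatic impairment. Closer monitoring is advised, exclusion 12 screens at entry, and the wording of Appendix A is attributed to the label. The Section 5.3 list concerns other anticancer and investigational treatments, so its silence shows little.

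Most of this stands and limits the point. It does not remove the conflict: a fallback that may be declined differs from a rule that bars the combination, and a label origin explains the softer wording without saying which text governs.

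Three stronger readings are tempting and not supported.

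- A reader might take AUC to rise up to 29-fold, because Section 2.2.3 says AUC to the last quantifiable concentration "was extended up to 29 times longer than without ketoconazole exposure". That sentence is garbled. Appendix A assigns 29 to Cmax and 24 to AUC, so only 24 is used here.
- A reader might treat the 24-fold ratio as the exposure expected in trial patients or with any strong inhibitor. The documents give it for ketoconazole in healthy volunteers, with no figure for voriconazole, posaconazole or clarithromycin. The hepatic ratios come from a separate single-dose study of a lasting condition.
- A reader might infer that any course beyond 7 days must end ibrutinib. Section 2.2.3 bars taking the two together; a hold for the length of the course satisfies it.

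**Conclusion.** The inconsistency is real and should be corrected. As written, a patient may stay on 560 mg of ibrutinib during a strong-inhibitor course of up to 7 days in compliance with Section 5.2.2, although Section 2.2.3 does not allow the combination and a moderate inhibitor forces a cut to 140 mg. The ketoconazole AUC ratio is 8.9 times the ratio at which 140 mg is named and 2.4 to 2.9 times those at which ibrutinib is to be avoided.

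The textual conflict needs no assumption. The ratios assume only that fold-changes from separate studies can be set side by side as a rough guide; no projection to steady-state exposure in patients is made. The documents do not say how many patients would need a strong inhibitor, so the number affected cannot be estimated. Nor do they support a quantified effect on the toxicity endpoint or its stopping rule.

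**What to change.** In Section 5.2.2:

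1. State that strong CYP3A inhibitors must not be taken together with ibrutinib, in line with Section 2.2.3.
2. Replace the optional hold with a mandatory one for any unavoidable course, whatever its length: *interrupt ibrutinib until the strong inhibitor has been stopped*.
3. Discontinue ibrutinib only if the need for the strong inhibitor is chronic.

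In Appendix A, either make the same change or add a note that the trial rule in Section 5.2.2 overrides the label wording. The note avoids attributing a trial-specific rule to the label under the present heading. Keep the closer-monitoring sentence, including strong inhibitors, so that inadvertent exposure is still followed up.

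The change is wording in two places. For the patient, a 7-day course costs up to 7 ibrutinib doses, 25% of a cycle or about 2% of 12 cycles, and a longer course costs proportionately more. A patient with a chronic need loses ibrutinib.
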